****3. Sample Size Calculation:****

$$\text{Formula: } n = [(Z \alpha / 2 + Z \beta) * \sigma / \Delta]^2$$

Where n is the sample size, $Z \alpha / 2$ is the two-sided quantile of the normal distribution corresponding to the significance level α (usually $\alpha = 0.05$, so $Z \alpha / 2 = 1.96$). $Z \beta$ is the quantile

of the normal distribution corresponding to the power ($1 - \beta$) (power is usually set at 0.8, so $Z\beta = 0.84$). σ is the standard deviation of the observation indicator, reflecting data dispersion. Δ is the expected mean difference before and after treatment, i.e., the minimum difference expected to be detected. Based on literature review and preliminary studies, we set $\sigma = 4$ and $\Delta = 2$. Therefore, the calculated sample size $n = 31.36$. Rounding up, $n=32$. Considering potential dropouts, the sample size needs to be increased by 10%-20%, so the final sample size is set at 80.

4. Data Analysis and Statistical Methods:

Conduct statistical analysis on the obtained data: Measurement data conforming to a normal distribution will be expressed as mean \pm standard deviation ($\bar{x} \pm s$). Count data will be expressed as frequencies. Comparisons of means before and after treatment will be performed using paired-sample t-tests. Comparisons of rates before and after treatment will be performed using chi-square tests. A P-value < 0.05 will be considered statistically significant.

Study Flowchart:

Patient Screening

↓

Collection of Patient Clinical and Laboratory Data

↓

Oral Administration of Dipyridamole Tablets under Guidance

↓ (12 weeks)

Collection of Drug-Related Adverse Reactions during the Study

↓

Post-Treatment Collection of General Clinical Data and Laboratory Parameters

↓

Statistical Analysis, Efficacy Evaluation, Manuscript Preparation

5. Safety Analysis and Content Evaluation:

Follow up and statistics on the types, number of cases, and severity grading of potential adverse reactions during dipyridamole treatment. Evaluate the causes of these adverse reactions and their causal relationship with the study drug. Calculate the incidence of adverse reactions. Main adverse reactions may include headache, dizziness, gastrointestinal discomfort (nausea, vomiting, diarrhea), hypotension, bleeding tendency, allergic reactions, etc.

6. Observation Indicators:

Primary Indicators: Restless Legs Syndrome symptom severity score (IRLS).

Secondary Indicators: Quality of life score (KDQOL-SF-36), Clinical Global Impression scale (CGI) score, Medical Outcomes Study Sleep Scale (MOS-SS) score, Pittsburgh Sleep Quality Index (PSQI) score, Epworth Sleepiness Scale (ESS) score, Hamilton Anxiety Rating Scale (HAMA) score, Hamilton Depression Rating Scale (HAMD) score, Self-Rating Anxiety Scale (SAS) score, Self-Rating Depression Scale (SDS) score.

Safety Indicators:

- ① Occurrence of adverse reactions: including but not limited to headache, dizziness, gastrointestinal discomfort (nausea, vomiting, abdominal pain, diarrhea), hypotension, bleeding

tendency (gingival bleeding, epistaxis, subcutaneous bruising, etc.), allergic reactions (rash, pruritus, dyspnea, etc.).

② Laboratory parameter monitoring:

* Hematological indicators: Regularly test complete blood count (including red blood cell count, hemoglobin, platelet count, etc.) and coagulation function (prothrombin time, activated partial thromboplastin time, fibrinogen, etc.) to monitor whether dipyridamole's antiplatelet aggregation effect increases bleeding risk or causes hematological abnormalities.

* Biochemical indicators: Test liver and kidney function parameters (e.g., ALT, AST, serum creatinine, blood urea nitrogen, etc.) to assess the drug's impact on liver and kidney function; monitor electrolytes (e.g., potassium, sodium, chloride, etc.) to observe if drug effects or changes in uremia condition lead to electrolyte disturbances.

③ Vital signs monitoring:

* Monitoring content: Regularly measure patients' blood pressure, heart rate, respiratory rate, body temperature, and other vital signs, with particular attention to blood pressure changes, alert for hypotension caused by the vasodilatory effect of dipyridamole.

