****III. Study Design and Methods:****

****1. Study Population:**** This is a single-center, self-controlled study. We plan to recruit 80 patients with uremia and RLS who are undergoing maintenance hemodialysis at the Blood Purification Center of the First Affiliated Hospital of Chongqing Medical University from July 2025 to December 2025.

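### The target of 80 patients does not follow from the protocol's own sample size calculation, which leads to 36 to 40

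*Protocol*

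**What the plan says.** Section III.3 of the protocol uses the one-sample (paired) formula for a mean, with two-sided alpha 0.05, power 0.8, sigma = 4 and Delta = 2. It obtains 31.36 and rounds up to 32. It then concludes: "Considering potential dropouts, the sample size needs to be increased by 10%-20%, so the final sample size is set at 80".

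The inputs are described as follows:
- Sigma "is the standard deviation of the observation indicator, reflecting data dispersion".
- For Delta, the protocol takes the smallest before-after change in the mean that the trial should be able to detect.
- The only source given is the phrase "Based on literature review and preliminary studies, we set" these values. The paragraph does not name the outcome.

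Section III.1 states the design, "This is a single-center, self-controlled study", and repeats the target: "We plan to recruit 80 patients with uremia and RLS". Sections III.2(7) and III.4 analyse before-after means with a paired t-test. Section III.6 gives the restless legs severity score (IRLS) as the primary indicator, while section III.2(8) lists remission, response, adverse-event and dropout rates as primary.

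**The concern.** The last sentence of the calculation presents 80 as the result of a 10% to 20% dropout allowance on 32, and that step does not produce 80. The printed rationale (80% power, 32 evaluable patients, 10% to 20% dropout) therefore describes a trial about half the size of the one planned. A reader or an ethics committee cannot tell what 80 was chosen to achieve.

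The wording of sigma adds to this. In the printed formula sigma has to be the SD of the within-patient change. The text describes it as the SD of an indicator, which could equally be the spread of scores at a single visit. Under the first reading, 80 is about twice the derived need, so about twice as many patients as justified would be exposed to the study drug. Under the second, 80 may be roughly what is needed, and 32 would be far too few.

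**Working it through.** **Inputs from section III.3:** z = 1.96 (two-sided alpha 0.05), z = 0.84 (power 0.8), sigma = 4, Delta = 2, dropout 10% to 20%. Within-patient correlations r are not in the protocol; the values used below are assumptions.

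**1. The plan's own base figure.** [(1.96 + 0.84) × 4 / 2]² = 5.6² = 31.36, rounded up to 32. This reproduces.

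**2. The dropout step.**
- Multiplying: 32 × 1.1 = 35.2 → 36; 32 × 1.2 = 38.4 → 39.
- Dividing: 32 / 0.9 = 35.6 → 36; 32 / 0.8 = 40.

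The result is 36 to 40. The stated 80 does not reproduce: 80 / 32 = 2.5 (an increase of 150%), and 1 − 32/80 = 0.60 (a 60% dropout allowance).

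**3. Other routes to 80.**
- Power of 90% gives 43, or 48 to 54 with dropout.
- Power of 95% gives 52, or 58 to 65 with dropout.
- Doubling 40 for two groups gives 80, but the design has one group.
- Reading sigma as a single-visit SD with r = 0 gives an SD of change of 4 × √2 = 5.657 and a base of (2.8 × 5.657 / 2)² = 62.72 → 63. With dropout this is 70 to 79, close to 80. The protocol neither states nor computes this; it prints 32.

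**4. What 80 delivers under each reading of sigma.** For a single-visit SD of 4, the SD of change is 4 × √(2(1 − r)): 5.657 at r = 0, 4.899 at r = 0.25 and 4.000 at r = 0.5. The last is the same as reading sigma as the SD of change.

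Power of the two-sided paired t-test (noncentral t) for a 2-point change, by number analysed (64, 72 and 80 are 80 less 20%, less 10% and with no dropout):

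| Reading of sigma = 4 | SD of change | 32 | 64 | 72 | 80 |
|---|---|---|---|---|---|
| SD of change | 4.000 | 78.2% | 97.6% | 98.7% | 99.3% |
| Single-visit SD, r = 0.25 (assumed) | 4.899 | 60.9% | 89.5% | 92.7% | 95.0% |
| Single-visit SD, r = 0 (assumed) | 5.657 | 49.1% | 79.5% | 84.1% | 87.8% |

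Change detectable with 80% power, in points:

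| Reading of sigma = 4 | 64 | 72 | 80 |
|---|---|---|---|
| SD of change | 1.42 | 1.34 | 1.27 |
| Single-visit SD, r = 0.25 (assumed) | 1.74 | 1.64 | 1.55 |
| Single-visit SD, r = 0 (assumed) | 2.01 | 1.89 | 1.79 |

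**5. Exact base.** The paired t-test reaches 80% power at 34 patients for an SD of change of 4, slightly more than the normal-approximation figure of 32. With dropout: 34 × 1.1 = 37.4 and 34 / 0.9 = 37.8, both → 38; 34 × 1.2 = 40.8 → 41; 34 / 0.8 = 42.5 → 43.

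**The case against.** The strongest reply is that sigma is not really ambiguous. The formula is the paired one, Delta is a before-after difference and the test is a paired t-test, so sigma can only be the SD of the change. A single-visit reading needs a factor 2(1 − r) that the formula does not contain, and r = 0 for two scores from the same patient is extreme. Section III.6 also suggests that the unnamed indicator is the IRLS. On this view power is simply 98% to 99%, the discrepancy errs towards more patients, and nothing in the analysis changes.

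Part of this stands. On the formula as printed, the SD of change is the natural reading. The r = 0 and r = 0.25 rows are assumed cases that bound the uncertainty and are not estimates. No shortfall in power is shown.

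The reply does not settle what the value 4 is. The formula shows what sigma ought to be; the text describes it as something else, with no source that can be checked. The link to the IRLS is likely but not certain, because secondary scores also fall under section III.6 and section III.2(8) names rates as primary. Nor does the reply touch the main point: 32 plus 10% to 20% is not 80 under any reading of sigma. A protocol may leave detail to a statistical analysis plan, but here it prints a derivation, and that derivation is wrong.

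**Conclusion.** The concern holds and should be fixed. By the protocol's own inputs the enrolment target is 36 to 40, against a stated 80, and no other basis for 80 is given. This conclusion needs no outside assumption.

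It is an error of justification, not of validity. If sigma = 4 is the SD of change, the trial enrols about twice the derived number. If it is a single-visit SD, the answer depends on a correlation that the protocol does not give; with any non-negative correlation, 80 enrolled still gives about 80% power or more after 20% dropout.

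**What to change.** Keep 80 and rewrite the paragraph in section III.3:

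1. Delete the step from the 10% to 20% allowance to 80, and state the sponsor's actual reason for 80.
2. Confirm from the sponsor's source, and then state, which outcome sigma = 4 describes and whether it is the SD of the within-patient change or of a single-visit score.
3. Restate what 80 delivers. If sigma is the SD of change, wording such as: *With 64 to 80 evaluable patients, power is about 98% to 99% for a 2-point change, and a change of about 1.3 to 1.4 points is detectable with 80% power.* If it is a single-visit SD, give the within-patient correlation and its source, use SD of change = 4 × √(2(1 − r)), and report the resulting power.

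This costs one paragraph and one source check, with no extra patients and no design change.

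Only if sigma is confirmed as the SD of change could the target be lowered instead: to 36 to 40 on the protocol's own base of 32, or preferably 38 to 43 on the exact paired-t base of 34. Sections III.1 and III.3 would then both change. The price is less precision for the rates listed as primary in section III.2(8). For a rate of 50% (assumed, the widest case), the approximate 95% half-width is 1.96 × 0.5 / √80 = 11 percentage points with 80 patients. It is 1.96 × 0.5 / √43 = 15 points with 43, and 1.96 × 0.5 / √38 = 16 points with 38. Without that confirmation the target should not be cut.

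### The only comparison stated for continuous data, a paired t-test of before and after means, does not answer whether individual patients develop laboratory abnormalities on treatment

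*Protocol*

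**What the plan says.** III.4 gives one general set of rules for the data obtained, and III.2(7) gives nearly the same set. "Measurement data conforming to a normal distribution will be expressed as mean" with its standard deviation, and "Count data will be expressed as frequencies". For testing, "Comparisons of means before and after treatment will be performed using paired-sample t-tests" and "Comparisons of rates before and after treatment will be performed using chi-square tests" (III.2(7) specifies a paired chi-square). No other comparison for continuous values appears in the protocol. Neither section names laboratory values or blood pressure, and neither exempts them.

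III.6 lists three kinds of safety indicator: adverse reactions, laboratory parameters and vital signs. Blood counts and coagulation are tested regularly "to monitor whether dipyridamole's antiplatelet aggregation effect increases bleeding risk or causes hematological abnormalities". Electrolytes are monitored for disturbances. For vital signs the instruction is "Regularly measure patients' blood pressure, heart rate, respiratory rate, body temperature, and other vital signs", with an alert for hypotension.

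III.5 plans a separate safety analysis of adverse reactions during treatment: type, number of cases, severity grade, causality and incidence. Hypotension and bleeding tendency are among its examples. III.2(3) and III.2(6) describe laboratory collection before treatment and again after it ends.

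**The concern.** The purpose stated in III.6 and the method stated in III.4 do not match. Whether a drug "increases bleeding risk or causes hematological abnormalities" is asked patient by patient, over the whole treatment period. The stated test asks whether the average patient differs between two time points. A large change in a few patients barely moves that average, and a change that has recovered by week 12 never enters it.

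III.5 covers part of the question, because recognised clinical events are counted and graded there. But it analyses adverse reactions only, its examples are clinical, and nothing says when an abnormal laboratory value becomes an adverse reaction. A symptom-free fall in platelets or hemoglobin, or a disturbed potassium, has no stated route into the incidence count. The same holds for a measured blood pressure fall that is not reported. Safety is part of the study objective and there is no control group, so the per-patient record is the main safety evidence the trial can give on these measures.

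**Working it through.** **Plan's own figure.** The protocol gives no figure on this point. Its sample size reproduces, [(1.96 + 0.84) × 4 / 2]² = 31.36, rounded up to 32, but that concerns a mean difference and does not bear on the issue. N = 80 is taken from III.3.

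**Which safety data have a per-patient analysis?**

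| Safety indicator (III.6) | Stated purpose | Stated analysis |
|---|---|---|
| Adverse reactions, including hypotension and bleeding tendency | Occurrence | Cases, severity, incidence (III.5) |
| Blood count, coagulation | Bleeding risk, abnormalities | General rule only: before/after means |
| Biochemistry, electrolytes | Liver and kidney effects, disturbances | General rule only: before/after means |
| Vital signs | Hypotension | Before/after means; per patient only if reported as an adverse reaction |

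The frequencies and rate test in III.4 could be applied to laboratory values only once an abnormal category is defined, and none is.

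**How insensitive is the mean?** Assumptions, none from the protocol: 4 of 80 patients lose 30 g/L of hemoglobin, the others do not change on average, and the SD of change is 10 g/L.

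1. Mean change: 4 × (−30) / 80 = −1.5 g/L.
2. SD of change over all 80: √(10² + 0.05 × 0.95 × 30²) = √142.75 ≈ 11.9 g/L.
3. Standard error: 11.9 / √80 ≈ 1.34 g/L, so a typical t is about 1.5 / 1.34 ≈ 1.1, against a critical value near 2.
4. Simulated two-sided paired t-test at 0.05: significant in about 15% of trials (about 19% with SD 8, 13% with SD 12).
5. Direct count: 4/80 = 5%, Clopper-Pearson 95% interval 1.4% to 12.3%.

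**Range at N = 80 (simulated, falls in units of the SD of change).**

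| Patients who fall | Significant, 3 SD fall | Significant, 4 SD fall |
|---|---|---|
| 1 | 5% | 5% |
| 2 | 7% | 8% |
| 4 | 15% | 20% |
| 5 | 22% | 30% |
| 8 | 50% | 68% |

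The test becomes useful only when about a tenth of patients are affected. For a fall that has recovered by week 12, the affected patients add nothing to the comparison, whatever its depth.

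**What does a worst-value count cost?** Assume the same SD of change of 10 g/L, independent values around each patient's own mean, and a purely illustrative cut-off of a 20 g/L fall. Patients with no true change cross it in 2.3% of cases with one on-treatment test, 5.7% with three and 9.6% with six. The count is therefore inflated by the number of tests, and the proposal has to allow for that.

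**The case against.** The strongest reply has four parts.

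*The sentence is a general rule, and frequencies and a rate test are stated beside it.* True. Counting patients with abnormal values would be compatible with III.4. But no category is defined for these values, so as written only the mean comparison can be carried out.

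*Serious falls are not hidden.* A reader might infer that the plan conceals serious harm in a few patients. The documents do not support that. III.5 counts and grades hypotension and bleeding tendency during treatment, and III.2(8) lists adverse event incidence among the primary evaluation indicators. A hypotensive episode that recovers is countable if it is reported. What stands is the narrower gap: symptom-free laboratory changes and unreported blood pressure falls. Nor does any section say that P above 0.05 will be read as evidence of safety.

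*Repeated laboratory values may not exist.* In III.6 the word regularly is attached to blood count, coagulation and vital signs, not to biochemistry, and III.2 names only a pre-treatment and a post-treatment laboratory collection. So it cannot be said that a full set of on-treatment values is being ignored. This stands, and is itself something to reconcile.

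*Shift tables and abnormality limits belong in a SAP, which may exist.* Their absence alone would be no finding. The point here is that the comparison the protocol does state does not fit the purpose the protocol states.

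It is also fair that a simple normal/abnormal shift would miss patients already abnormal at baseline, which is likely for several measures in a dialysis population. The fix is worded accordingly.

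**Conclusion.** The point holds in a limited form and should be acted on. The paired comparison of means does not answer the laboratory safety questions set in III.6, and III.5 closes the gap only for events recognised as adverse reactions. In the illustration the test detects the pattern in roughly 13% to 19% of trials, while a count reports 5% with an interval of 1.4% to 12.3%. These two quantities are not on the same scale: one is the power of a test, the other an estimate with its precision. The SD, the number of patients and the size of the fall are all assumed. The qualitative conclusion, that a mean is insensitive to large changes in a few patients, does not depend on the exact values. No sample size or power figure in the protocol changes.

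**What to change.** In III.4 or III.5, for each safety laboratory value and blood pressure:

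- Keep the before/after means as description.
- Add the number and percentage of patients who worsen from their own baseline during treatment, with an exact 95% interval. Fix the qualifying change or category before the data are seen, and choose it so that patients already abnormal at baseline can also qualify.
- Show a table of baseline against worst on-treatment value, and beside it the end-of-treatment value, so that extra tests do not inflate the count unseen.
- State that qualifying values enter the adverse reaction count in III.5.
- Reconcile the regular testing in III.6 with the before/after laboratory collection in III.2(3) and III.2(6). If only two laboratory time points are recorded, apply the count to the week-12 value.

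The cost is some wording and a few more tables. Section VII says patients are already under regular laboratory follow-up at the centre, so little extra testing should be needed, but the sponsor should confirm which values are recorded. The downside is that worst-value counts include random variation that grows with the number of tests, so the reported frequency will look less favourable.

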****IV. Study Risks and Benefits:****

****Study Risks:**** During dipyridamole treatment, patients may experience adverse events such as bleeding, including gastrointestinal bleeding, cerebral hemorrhage, subcutaneous bleeding, gingival bleeding, etc. If these occur, please inform the physician as soon as possible. The physician will take active intervention measures based on the specific situation to 尽量 ensure the protection of patient rights and interests. Furthermore, physicians will strictly maintain the confidentiality of patient medical records and information.

****Study Benefits:**** The relevant examinations and collection of medical history data will contribute to a comprehensive understanding of the patient's disease and provide an optimal treatment plan. Under guidance, taking dipyridamole tablets may improve the patient's RLS sensory and motor symptoms as well as sleep quality.

****Risk-Benefit Assessment:**** We predict that the benefits of this study significantly outweigh the associated risks.

****V. Subject Recruitment****

****1. Recruitment Method:**** This study will recruit patients through the Dialysis Unit of the Department of Nephrology at the First Affiliated Hospital of Chongqing Medical University. The research team will screen patients who meet the inclusion criteria. All subjects are patients actively seeking medical consultation at the Dialysis Unit of the Department of Nephrology; no additional recruitment advertisements will be used.

****2. Consideration Regarding Vulnerable Groups:**** This study strictly avoids recruiting vulnerable groups, including minors, pregnant women, prisoners, illiterate individuals, and individuals without capacity or with limited capacity. All subjects must be 18 years or older, have full capacity, be able to fully understand the study content, and provide signed informed consent.

****VI. Informed Consent Process:****

The informed consent process for this study will be strictly executed according to ethical norms, overseen by the project leader and research assistants to fully safeguard patient rights and the

right to informed consent.

- (1) **Implementers of Recruitment and Informed Consent:** The recruitment and informed consent process for this study is primarily the joint responsibility of the project leader and research assistants. Research assistants are responsible for preliminary screening of patients against the inclusion and exclusion criteria and assisting the project leader in communicating study details to patients.
- (2) **Specific Informed Consent Process:** After screening, the project leader or research assistant will conduct a face-to-face discussion with the patient, detailing the study's purpose, procedures, potential risks, and benefits, ensuring the patient fully understands the study. Provide the patient with a written informed consent form that is easy to understand, avoiding excessive technical terminology, ensuring the patient can read and comprehend it independently. Allow the patient ample opportunity to ask questions, and provide detailed answers to all queries, ensuring transparency and adequacy of the informed consent process.
- (3) **Requirements for the Informed Consent Subject:** All subjects must be adults aged 18 or older with full capacity; no proxy signatures are required. The research team ensures voluntary participation and will absolutely not exert any form of pressure or inducement for patients to participate.
- (4) **Avoiding Direct Recruitment by Treating Physician:** To avoid potential conflicts of interest or implicit pressure, the patient's treating physician will not participate in the informed consent process. Other members of the research team will communicate and explain the study content to the patient.
- (5) **Voluntariness and Withdrawal Guarantee:** The informed consent form clearly states that participation is entirely voluntary, and the patient can unconditionally withdraw from the study at any stage, which will not affect their subsequent medical care. If a patient chooses to withdraw, the research team will provide necessary medical advice and ensure a smooth withdrawal process without additional burden.
- (6) **Information Updates and Feedback:** If new information arises during the study that may affect patient rights or health, the project leader will promptly communicate with the patient and re-seek informed consent if necessary. Patients have the right to be informed about study-related information at any time, including research progress and data related to their own health status.

